- Overall study success criteria of at least a 30% difference between the test device group and the placebo group, comparing the proportion of individual successes in each group.
- It is anticipated that about 50% of subjects in the test device group and about 20% of subjects in the placebo group will meet the individual success criteria, and
- Intended application of a two-tailed test with an alpha value of 0.05 and Power of 0.8

- the sample size of 25 available subjects per group (test group and the control group, separately) has been determined using the following reference calculator: *Hypothesis Testing: Categorical Data - Estimation of Sample Size and Power for Comparing Two Binomial Proportions* in Bernard Rosner's *Fundamentals of Biostatistics*.

For the purposes of sample size calculation, a subject loss-to-follow-up of 20% is anticipated.

Therefore, a minimum starting sample size of 30 evaluable subjects in each group is needed to ensure that a sufficient number remains at the end of the trial (25 subjects per group) for any significant differences found between groups to be considered statistically valid and representative of the general population being sampled. This results in a total of 60 subjects being enrolled in this study across both study procedure groups.

RANDOMIZATION

Subject allocation to procedure group will be via variable block randomization with varying block sizes of two and four used at random to minimize the likelihood of predicting the next procedure group assignment. In addition, randomization will be stratified by Fitzpatrick Skin Type grouping

Randomization will be attained using computer generation sequence methodology, ensuring that the randomization methodology and the generated allocation sequence is concealed from the investigator and subjects.

Concealment will be insured as follows:

- Each computer-generated randomization sequence is unique and will therefore not be able to be replicated.
- Randomization will occur to either 'Test Group A' or 'B' rather than to a tests or placebo group, and only the study Sponsor will know which assignment corresponds to the active devices and which corresponds to the fake device. The Sponsor will not reveal this information to any source (investigators, subjects, or study Monitor) until the final study data analysis is complete.

TRIPLE BLIND DESIGN

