This clinical study will be a triple-blind design, such that neither the subject, nor the assessor, nor the therapists will be aware of whether a subject is receiving the study procedure with the active (test procedure group assignment) or the 'fake' (placebo procedure group assignment) Multi Radiance Medical MR5 Prototype Device until after the study is completed.

Maintenance of study triple-blind throughout the entire course of the study will be achieved through the following means:

- Each subject will be randomly assigned to 'Test Group A' or 'B' by the independent study Monitor. Only the study Sponsor will know which label 'Test Group A' or 'B' corresponds to the actual (test) MR5 device and which label corresponds to the 'fake' device until the final study data analysis is complete. The Sponsor will ensure that this information is stored and maintained confidentially at the Sponsor's work site. This knowledge will not be shared with the investigators, the subjects, or the study Monitor until the final data analysis is complete.
- The fake (placebo) MR5 device is designed to have the same physical appearance as the actual MR5 device, including the appearance of any **visible** light output. Therefore, both the test and sham devices emit light when activated that is indistinguishable to both

the subject and to the investigator. As the laser light does not put out any notable degree of heat or noise, these are not distinguishing factors for subjects between the four groups.

3) There will be two independent investigators interacting with subjects at each test site:

- Administration investigator*: who will be responsible for administrating the study procedures; and
- Assessment investigator*: who will be responsible for recording the study outcome measures

Only the administration investigator will be aware of whether a subject is assigned to 'Test Group A' or 'B', although he or she will not be made aware of whether 'Test Group A' or 'B' corresponds to the true or fake laser. Neither the assessment investigator nor the subject will be aware of the subject's A/B Group assignment. In this way, the assessment investigator will not be able to form an association between A/B Procedure Group and active/sham device over the course of the study if a treatment effect is observed.

4) During the MR5 procedures, both the subject and the administration investigator will wear Laser Safety Industries protective eyewear that filter out the laser light spectrum.

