TABLE OF SUBJECT EVENTS

The following table provides a progressive summary of subject events throughout this study.

PRE-PROCEDURE ACTIVITIES	
1. A potentially well-suited and interested candidate for participation in the study attends the investigator's office.	
2. The investigator reviews the informed consent form with the candidate.	
3. If the candidate continues to be interested and voluntarily signs the informed consent form, the study qualification evaluation phase of the study is performed.	
4. A qualified subject is randomly assigned to procedure group.	
5. One-week individualized pain management regimen stabilization phase occurs	
6. The following measures are recorded during the Stabilization Phase: 
▪ Subject Daily Diary▪ Degree of Pain Ratings on final three days	
PRE-PROCEDURE ASSESSMENT PHASE	
CONTINUED STUDY ELIGIBILITY EVALUATION	

▪ Review of application of individualized pain management regimen throughout the Stabilization Phase▪ Evaluation of 3-day average VAS rating	
PRE-PROCEDURE MEASURES	

▪ Degree of Pain Rating▪ PRTEE, Grip Strength and TNFa measurements	
PRE-PROCEDURE VARIABLES	

▪ Baseline concomitant medication and treatment/therapy use	

- Historical pain medication and treatment/therapy use
- Baseline Lateral Epicondylitis pain variables
- Demographics

PROCEDURE ADMINISTRATION PHASE

Six 9-minute study procedure administrations with the Multi Radiance Medical® Prototype Device, two procedure administrations a week for three consecutive weeks administered at the test site.

PROCEDURE ADMINISTRATION PHASE MEASURES

DAILY THROUGHOUT THE THREE-WEEK PROCEDURE ADMINISTRATION PHASE

- Maintenance of the individualized pain management regimen, as needed
- Subject Daily Diary

WITHIN 24 HOURS OF COMPLETION OF THE FINAL PROCEDURE ADMINISTRATION

- Degree of Pain Rating
- PRTEE, Grip Strength and TNFa measurements
- Subject Satisfaction with Overall Outcome Rating
- Perceived Group Assignment
- Investigator Adverse Events Evaluation

POST-PROCEDURE ADMINISTRATION PHASE

DAILY THROUGHOUT THE ONE MONTH POST-PROCEDURE ADMINISTRATION PHASE

- Maintenance of the individualized pain management regimen, as needed
- Subject Daily Diary

ONE MONTH (30 DAYS) POST-PROCEDURE ADMINISTRATION PHASE (TEST SITE VISIT)

- Degree of Pain Rating
- PRTEE, Grip Strength and TNFa measurements

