- Pregnant, breast feeding, or planning pregnancy prior to the end of study participation
- Serious mental health illness such as dementia or schizophrenia; psychiatric hospitalization in past two years
- Developmental disability or cognitive impairment that in the opinion of the investigator would preclude adequate comprehension of the informed consent form and/or ability to record the necessary study measurements
- Involvement in litigation and/or receiving disability benefits related in any way to the parameters of the study
- Subject is less than 18 years of age
- Participation in a clinical study or other type of research in the past 30 days
- Subject is not fluent in Portuguese

SUBJECT GROUP RANDOMIZATION

A fully qualified subject is randomly assigned to 'Test Group A' or 'B' following the methodology outlined above in the STUDY DESIGN section of the protocol.

INDIVIDUALIZED PAIN MANAGEMENT REGIMEN STABILIZATION PHASE:

During the one-week period immediately preceding commencement of the pre-procedure assessment phase, subjects will partake in a pain management stabilization phase. See **Appendix C** for Individualized Pain Medication Regimen Details.

ESTABLISHMENT OF PROCEDURE ADMINISTRATION VISIT SCHEDULE

To implement consistency in the time of day when VAS pain ratings are recorded across all evaluation points throughout the study duration, the visit schedule times for each of the six procedure administration visits will be established at this time within a one-hour time frame. For example, between 2 p.m. and 3 p.m. for each of the six procedure administration visits, or between 10 a.m. and 11 a.m. for each of the six procedure administration visits, etc.

INDIVIDUALIZED PAIN MANAGEMENT REGIMEN STABILIZATION PHASE MEASURES

During the two-week stabilization phase, the subject records the following, as applicable.

- Subject Daily Diary
- Degree of Pain Rating on the 0-100 VAS on each of the last three days of the baseline stabilization phase, each measurement to be recorded within 15 minutes of the procedure administration visit times scheduled. For example, if the procedure administration visit schedule is established as between 2 p.m. and 3 p.m., the latest time a required VAS recording can be made is 3:15 p.m. The subject will record the exact time that he or she marks the VAS recording.

PRE-PROCEDURE ASSESSMENT PHASE

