The pre-procedure assessment phase will commence following successful completion of the individualized pain management regimen stabilization phase and just prior to commencement of the procedure administration phase.

CONTINUED STUDY ELIGIBILITY EVALUATION

Prior to the subject commencing the Pre-Procedure Assessment phase of the study, the investigator will:

- review the subject's recordings of use/application of his or her individualized pain management regimen to ensure it was correctly applied and recorded, and that there are no deviations significant enough to warrant withdrawal of the subject from the study prior to entry to the pre-procedure assessment phase; and
- calculate the average of the 3 VAS degree of pain scores recorded during the last three days of the individualized pain management regimen stabilization phase. In order for the subject to proceed, the 3-day average VAS score must be 50 or greater. If it is less than 50, the subject's participation in the study ends at this time.

PRE-PROCEDURE MEASURES

- Degree of Pain Rating. This will occur within 15 minutes prior to the initial procedure administration. The exact time the VAS rating is recorded will be noted.
- PRTEE, Grip Strength and TNFa measurements will be noted.

PRE-PROCEDURE VARIABLES

- Baseline concomitant medication and treatment/therapy use
- Historical pain medication and treatment/therapy use
- Baseline Lateral Epicondyle pain variables
- PRTEE, Grip Strength and TNFa measurements and Fitzpatrick Skin Type Classification will be noted.
- Demographics

PROCEDURE ADMINISTRATION PHASE

PROCEDURE ADMINISTRATION PROTOCOL

- The procedure administration phase of the study will commence within 15 minutes subsequent to completion of the pre-procedure assessment phase.
- The procedure administration phase comprises a total of six procedure administrations with the Multi Radiance Medical® MR5® Prototype Device: two

procedures a week for three consecutive weeks*, each procedure administration three to four days apart.

[figure not shown]
- *Three weeks, 2 times a week... Follow-up at 4th week after administration phase*

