- Each of the six procedure administration visits will occur within the same on-hour timeframe, as explained above under 'ESTABLISHMENT OF PROCEDURE ADMINISTRATION VISIT SCHEDULE' above.
- Each procedure administration lasts 20 minutes.
- The procedure administrations with the MR5® Laser is administered by the procedure administrator at the test site.
- Prior to administration of treatment protocol skin should be cleansed and verify there is no broken skin.

The study procedure administration protocol is as follows:

1. The subject enters the procedure administration room and is situated in a seated position.
2. The skin should be prepared for treatment by cleansing skin and verification of no broken skin.
3. The subject is correctly fitted with the safety glasses.
4. The procedure administrator puts on the safety glasses and selects the Multi Radiance Medical® MR5® Prototype Device A or B according to the subject's procedure group randomization.
5. The Prototype Device emitter is statically held by direct contact with the skin on each of the target areas:
Identified in diagram (over the Lateral Epicondyle) for the light administration phase for 60s each location.
6. The total procedure administration duration is 5 minutes for the laser portion of the treatment.

Laser

	1 SPL	IR	Red	Total
Photons/sec	5.69E+15	1.10E+18	6.75E+17	1.78E+18
Time, sec	Irrad, W/cm2	0.002841	0.0625	0.05 1.15E-01
60 Energy, J		0.075	15	12 2.71E+01
Fluence, J/cm2	0.170455		3.75	3 6.92E+00

PROCEDURE ADMINISTRATION PHASE MEASURES

Daily throughout the three-week procedure administration phase, the subject will continue at home to:

- maintain application of his or her individualized pain management regimen, as during the two-week stabilization phase, and
- complete the Subject Daily Diary, as applicable

WITHIN 24 HOURS OF COMPLETION OF THE FINAL (6TH) PROCEDURE ADMINISTRATION

- Degree of Pain Rating. The exact time the VAS rating is recorded will be noted.
- PRTEE, Grip Strength and TNFa measurements will be noted.
- Subject Satisfaction with Overall Outcome Rating
- Perceived Group Assignment
- Investigator Adverse Events Evaluation

POST-PROCEDURE ADMINISTRATION PHASE

The post-procedure administration phase encompasses the one-week period immediately following completion of the procedure administration phase and comprises the following evaluation points and associated measures.

POST-PROCEDURE ADMINISTRATION PHASE EVALUATION POINTS AND MEASURES

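### Randomization comes before the second pain check, so randomized subjects can leave untreated; the set called ITT then omits them while the safety denominator counts them

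*Combined protocol and SAP*

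**What the plan says.** The order of events is the same in two places. In the Table of Subject Events, step 4 reads "A qualified subject is randomly assigned to procedure group", and stabilization is step 5. In the procedure text, Subject Group Randomization stands ahead of the stabilization section, which says: "During the one-week period immediately preceding commencement of the pre-procedure assessment phase, subjects will partake in a pain management stabilization phase". (Other lines call this phase two weeks long. Those passages need reconciling, but this point does not depend on the length.)

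The Continued Study Eligibility Evaluation comes next and has two exit routes:

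- **Pain score.** "In order for the subject to proceed, the 3-day average VAS score must be 50 or greater"; otherwise participation ends there.
- **Regimen review.** The investigator confirms "that there are no deviations significant enough to warrant withdrawal of the subject from the study".

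Both routes operate before any procedure. The assignment is first used later, at step 4 of the procedure administration protocol, when the administrator selects "Prototype Device A or B according to the subject's procedure group randomization".

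Two analysis sets are then defined. Under Primary Efficacy Outcome Statistical Evaluation Methods, the ITT set needs randomization, a valid baseline visit with the VAS recordings, and receipt of the first procedure. Under Safety Analyses, the set is everyone randomized to either group.

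**The concern.** A subject can be randomized and then removed by an eligibility rule before receiving anything. Nothing in the stabilization phase depends on the arm, so these post-randomization exclusions are avoidable.

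The two labels then work the wrong way round. The set named ITT leaves out randomized subjects who were never treated. The safety set, which should describe exposed subjects, includes people who never met the device. The planned missing-data methods (LOCF, tipping point, multiple imputation) do not help, because these subjects are outside the set to which they apply.

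At stake are a correctly named primary set and undiluted adverse event percentages in a study meant to support a De Novo submission. A smaller issue is the regimen review. It is a judgement made after A/B labels exist. The section says only that the investigator makes it, while Triple Blind Design says: "Only the administration investigator will be aware of whether a subject is assigned to" A or B.

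**Working it through.** **Step 1. Trace a subject who screens in at VAS 50 or more and then fails the 3-day average.**

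| Stage | Status |
|---|---|
| Qualification (single VAS at least 50) | passes |
| Randomization | assigned A or B |
| Stabilization, then 3-day average | below 50, participation ends |
| First procedure | not received |
| Set called ITT | excluded |
| Safety set | included |

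The same path applies to a subject withdrawn for regimen deviations.

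**Step 2. How often might this happen?** The documents give no rate, so this step rests on assumptions. For the population presenting at screening, before the first VAS rule is applied, take a normal VAS with mean 55 to 75, between-subject SD (B) 12 or 15, and independent day-to-day SD (W) 10 or 15.

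- Variance of the single screening rating: B² + W²
- Variance of the 3-day mean: B² + W²/3
- Covariance of the two: B²
- Exit rate f = P(3-day mean < 50 and screening ≥ 50) / P(screening ≥ 50), from the bivariate normal

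Worked corner, mean 55, B = 12, W = 15: the variances are 144 + 225 = 369 and 144 + 75 = 219, and the correlation is 144/√(369 × 219) = 0.507. This gives f = 23.8%. In this corner about 40% of those presenting already fail the first check, so it is an extreme case.

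| Mean VAS before screening | f, lowest to highest over the SDs |
|---|---|
| 55 | 16.0% to 23.8% |
| 60 | 11.2% to 16.0% |
| 65 | 6.6% to 10.8% |
| 70 | 3.5% to 7.1% |
| 75 | 1.7% to 4.3% |

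A second set of assumptions (mean 55 to 65, total SD 15 to 20, correlation between single ratings 0.6 to 0.8) gives 5% to 19%. Neither calculation covers exits for regimen deviations, for which there is nothing to model.

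**Step 3. Chance that the problem arises at all.** If 60 are randomized, P(at least one exit) = 1 − (1 − f)^60. This is 63% at f = 1.7%, 98% at 6.6%, and above 99% at 11.2%.

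**Step 4. Effect on the safety table.** If a proportion r of treated subjects have an adverse event and untreated exits have none, the table shows about r(1 − f). The relative understatement is f, roughly 2% to 24% over the range above. The factor is expected to be the same in both arms, so the ratio between arms is unchanged and the absolute difference shrinks by the same factor.

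**Step 5. Bias.** Exits precede any procedure. The subject and the assessment investigator do not know the A/B label, and the administration investigator knows the label but not which one is active. Exit on the VAS average should therefore be unrelated to arm. Only the regimen review leaves an opening, and a small one.

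**The case against.** The strongest reply is that nothing here threatens validity. The exits are masked and occur before treatment. The plan states the conditions of its ITT set openly, so nobody is misled about who is analysed. Safety dilution falls on both arms alike, and few adverse events are expected. Appendix C is not in the text reviewed and may define which deviations are significant. The absence of a stated reason for early assignment is not an error.

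Most of this stands, and it limits the severity. It does not remove the mislabelled set, the unexposed subjects in the safety denominator, or the fact that both can be avoided at little cost.

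A reader might also infer that these exits erode power. The plan says "For the purposes of sample size calculation, a subject loss-to-follow-up of 20% is anticipated", and 30 × 0.80 = 24 is already below the stated 25, so there seems to be no room for further losses. The documents do not support that inference:

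- The Sample size section describes 60 subjects evaluated for eligibility.
- The rationale asks for "a minimum starting sample size of 30 evaluable subjects in each group is needed to ensure that a sufficient number remains at the end".
- The skin-type quotas refer to a final 50, and the site tables sum to 24 + 14 + 12 = 50.

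What 60 and 50 count is unclear, and no text says that an exit at this check goes unreplaced. Even without replacement, exact Fisher power for 50% v 20%, averaged over random exits, is 61.3% at an exit rate of 1.7%, against 59.6% at 30 per arm with no exits. At low rates power is therefore not lower. The gap between 59.6% and the planned 80% is a separate sample-size question.

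**Conclusion.** The point holds as one of sequence and set definition. Randomized subjects can leave untreated at the second check. They then fall outside a set that is modified ITT in all but name, and stay in a safety denominator that should count exposed subjects.

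The frequency is unknown. The range of about 2% to 24% depends wholly on the assumed VAS means and SDs; at means of 70 to 75 it is 1.7% to 7.1%. Even at the lowest rate, at least one such subject among 60 is more likely than not.

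Two stronger readings should be set aside. The first is that the treatment comparison is biased: the masking and timing give no ground for this beyond the small risk in the regimen review. The second is that power is lost: that needs an assumption of no replacement which the documents do not establish. Severity is minor to moderate.

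**What to change.** Keep both eligibility checks exactly as written, and:

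1. Release the A/B assignment after the Continued Study Eligibility Evaluation and before the first procedure. The skin-type stratum must be recorded by then; at present Fitzpatrick type is listed among the pre-procedure variables, after randomization.
2. Define ITT as all randomized subjects.
3. Define the safety set as all subjects who received at least one procedure.

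If assignment must stay at qualification, call the present set modified ITT, base safety on treated subjects, have someone who does not know the A/B label make the regimen review, and report untreated exits by arm with the reason.

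The cost is mainly wording. The Monitor must release assignments at that visit at three sites. This can be done during the pre-procedure assessment, before the 15-minute limit for starting the procedure phase begins to run. Recruitment is affected in one of two ways. To randomize 60, 60/(1 − f) must enter stabilization, which is 61 to 79 over the assumed range. If instead 60 enter, the number randomized is restated as 60(1 − f), about 59 to 46. The second option brings no gain in power; its benefit is correct analysis sets and no exclusions at this check after randomization.

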Daily throughout the one-week post-procedure administration phase, the subject will continue at home to:

- maintain application of his or her individualized pain management regimen, as during the two-week stabilization phase and the three-week procedure and phase, and
- complete the Subject Daily Diary, as applicable

ONE MONTH POST-PROCEDURE ADMINISTRATION PHASE (TEST SITE VISIT)

- Degree of Pain Rating: This time will be within the same one-hour time-frame as the prior post-procedure administration phase VAS ratings were recorded, 1 month after the final procedure administration; e.g., if the prior 3 post-procedure administration VAS recordings were made between 1:30 p.m. and 2:30 p.m. on each of the three days, then the 1 week post-procedure VAS recording will also be made between 1:30 p.m. and 2:30 p.m. The exact time the VAS rating is recorded will be noted.
- PRTEE, Grip Strength and TNFa measurements will be noted.
- Subject Satisfaction with Overall Outcome Rating
- Perceived Group Assignment
- Investigator Adverse Events Evaluation

ADVERSE EVENTS

At each evaluation and measurement point throughout the clinical study, and at any other time throughout the duration of the clinical trial that is necessary, any and all potential adverse events reported by a subject or observed by an investigator will be recorded on the case report form, and subsequently evaluated by the investigator for its relation to the study procedure and whether or not any corrective action needs to be taken. All potential adverse events recorded will be appropriately reported to the governing IRB, as applicable.

It is unlikely and not expected that any adverse events will result from implementation of this clinical study protocol. Prior clinical trials using low level laser light have not typically yielded any adverse events or reactions. However, potential adverse events that may feasibly occur from application of the Multi Radiance Medical® MR5® Prototype Device include, but are not necessarily limited to; skin irritation, discoloring, rash, indentations and infection.

PRIVACY AND CONFIDENTIALITY

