CHANGE IN SUBJECT SELF-REPORTED VAS PAIN RATING FROM BASELINE TO STUDY ENDPOINT

Primary efficacy outcome measure for this clinical study will be a statistically significant difference in the proportion of subjects between test and control groups who achieve a clinically meaningful and statistically significant decrease in self-reported VAS pain rating from baseline to study endpoint.

Subjects meeting Individual Success Criteria

The individual subject success criteria is defined as a 30% or greater decrease in self-reported VAS pain rating at study endpoint relative to baseline.

Overall Study Success Criteria.

Overall study success criteria is defined as at least a 30% difference between procedure groups, comparing the proportion of individual successes in each group. It is anticipated that about 50% of subjects in the test group will meet the individual success criteria and about 20% of subjects in the control group will meet the individual success criteria.

Evaluation Time Points

The study end evaluation time point at which study success will be analyzed is within 24 hours following completion of the three-week procedure administration phase with the Multi Radiance Medical® MR5® Prototype Device. Study success will be evaluated at endpoint relative to baseline.

Hypotheses

- *Null Hypothesis:* There will be no statistically significant difference in the proportion of individual successes, as defined, between the test and control groups.

- *Alternative Hypothesis:* There will be a statistically significant difference in the proportion of individual successes, as defined, between the test and control groups, to the effect of 30% or greater.

PRIMARY EFFICACY OUTCOME STATISTICAL EVALUATION METHODS

Intent to Treat (ITT) Principle: Primary efficacy analysis will be according to the intent to treat (ITT) principle; wherein subjects will be included in the analysis if they were randomized to study procedure group, had a valid baseline (pre-procedure) visit including the required Lateral Epicondylitis pain VAS recordings; and received at least the first study procedure administration.

Missing data will be handled through all of the following methods:

- *Last Observation Carried Forward (LOCF):* by carrying forward the last recorded observation to fill in the subsequent missing value.

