- *Tipping Point Analysis:* Tipping point analysis will be used to examine the impact of missing data on the study conclusion. Tipping point analysis is defined as the difference in means (for continuous data) or the difference in the number of events (for binary data) between treatment groups in the missing cohort at which the study conclusion is changed. A tipping point analysis replaces the missing value with other values so that the resulting p-value is equal to the pre-specified significance level (i.e. $\alpha=0.05$, 2-sided).
- *Multiple Imputation Analysis:* Multiple imputation analysis is a strategy to handle missing values in a clinical trials wherein each missing value is replaced with a set of plausible values that represent the uncertainty about the right value to impute. Multiple imputation does not attempt to estimate each missing value through simulated values, but rather to represent a random sample of the missing values. This process results in valid statistical inferences that properly reflect the uncertainty that results from missing values, such as valid confidence intervals for parameters.

Multiple imputation inference involves three distinct phases:

1. The missing data are filled in m times to generate m complete data sets.
2. The m complete data sets are analyzed by using standard statistical procedures.
3. The results from the m complete data sets are combined for the inference.

Multiple imputation usually assumes that the data are missing at random (MAR). That is, for a variable Y , the probability that an observation is missing depends only on the observed values of other variables, not on the unobserved values of Y .

Pre-Protocol Analysis will also be performed for the set of all subjects who were randomized to procedure group and completed the study according to the full protocol.

Primary analysis of efficacy will be according to intent to treat (ITT) analysis through the application of:

- 1) **Fisher's exact test** to compare the proportion of success between the test and the control groups, considering that randomization has been diligently conducted and important covariates between the two groups are well balanced.

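### The endpoint and one-month visits hang on the final or sixth procedure, so treated subjects who stop early stay in the primary analysis without a properly timed measurement

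*Combined protocol and SAP*

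**What the plan says.** The wordings below bear on who is analysed and when they are measured.

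- **Analysis set** (Statistical Analysis, Intent to Treat Principle): randomized, valid baseline, and "received at least the first study procedure administration". One procedure of six is enough.
- **Endpoint visit, procedure section** (Procedure Administration Phase Measures): VAS, PRTEE, grip strength, TNF-alpha, satisfaction, perceived group and the adverse event evaluation fall "WITHIN 24 HOURS OF COMPLETION OF THE FINAL (6TH) PROCEDURE ADMINISTRATION".
- **Endpoint visit, Table of Subject Events**: "WITHIN 24 HOURS OF COMPLETION OF THE FINAL PROCEDURE ADMINISTRATION", with no mention of the sixth.
- **Endpoint, statistical section** (Evaluation Time Points): "within 24 hours following completion of the three-week procedure administration phase". The Procedure Administration Protocol says that this phase "comprises a total of six procedure administrations", two a week for three weeks, three to four days apart.
- **Follow-up visit** (One Month Post-Procedure Administration Phase): "1 month after the final procedure administration".
- **Last VAS before the endpoint** (Pre-Procedure Measures): "This will occur within 15 minutes prior to the initial procedure administration".
- **Missing data**: last observation carried forward (LOCF), tipping-point analysis and multiple imputation are all listed. A separate per-protocol analysis covers those who "completed the study according to the full protocol".

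Withdrawal is mentioned only as a right in the consent process and as an eligibility check before treatment starts.

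**The concern.** The analysis set follows the intent-to-treat principle, but the measurement schedule follows treatment completion. A subject who has two procedures and then stops, but would gladly come back to be measured, belongs to the primary analysis. Under the most specific wording that subject has no scheduled endpoint. An outcome that could have been collected is then filled in by rule.

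The wordings also disagree, so sites could reasonably act differently on the same kind of subject. If stopping is related to lack of relief or to a local reaction, the resulting gaps are informative and may differ between arms. That matters in a trial planned at 30 per arm whose success criterion is a 30-point difference in responders.

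**Working it through.** **Step 1. Apply each wording to three kinds of treated subject.**

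| Subject | Final = sixth procedure | Final = last procedure received |
|---|---|---|
| Completes all six | Endpoint and one-month visit as planned | Same |
| Stops after procedure 1 to 5 | Trigger never reached: no endpoint, no one-month visit | Both visits exist but come too early |
| Misses one session, attends the last | No trigger if the sixth is taken literally | Endpoint as planned |

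The statistical section's wording could be read as a calendar time. Because the phase is defined by six procedures, it does not settle the matter.

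**Step 2. How early is too early?** Six procedures have five gaps of 3 to 4 days, so the sixth falls 5 × 3 = 15 to 5 × 4 = 20 days after the first. Under the last-received reading, a subject who stops after the first procedure has both visits 15 to 20 days ahead of a completer. Later stoppers are shifted less.

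**Step 3. What LOCF does under the no-endpoint reading.** The only scheduled VAS before the endpoint is the pre-procedure rating. Carrying it forward gives a 0% change, short of the 30% reduction needed, so the subject counts as a failure. This assumes that the daily diary holds no VAS rating; the diary and case report forms are not in the supplied text.

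**Step 4. Size, as a bounded illustration.** Inputs from Rationale for Sample Size: 50% v 20% responders, 30 starting per arm, 20% loss. The plan reaches 30 as 25 × 1.2. Taken as a share of 30, 20% is 6 subjects (24 left), while the plan's own step from 30 to 25 is 5.

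Assume a share *s* of each arm are treated early stoppers scored as failures, and the rest respond at the planned rates. Then each rate is multiplied by (1 − *s*). The last two columns use 30 per arm and exact enumeration of two binomials; power is for the two-sided 5% Fisher test.

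| *s* | Active v placebo | Difference | Fisher power | Chance of observing ≥ 30 points |
|---|---|---|---|---|
| 0 | 50% v 20% | 30 | 59.6% | 56.1% |
| 5% | 47.5% v 19% | 28.5 | 55.9% | 51.0% |
| 10% | 45% v 18% | 27 | 52.3% | 45.7% |
| 20% | 40% v 16% | 24 | 44.7% | 35.1% |

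With 5 of 30 lost instead of 6: 0.5 × 25/30 = 41.7% and 0.2 × 25/30 = 16.7%, a difference of 25 points. That power is below 80% even in the first row is a separate matter and plays no part here.

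**The case against.** The best defence has four parts.

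1. **A visit may exist.** The Table of Subject Events omits the word sixth, and the statistical section speaks of the three-week phase. On those wordings, a subject who misses a middle session but attends the last has an endpoint. This stands. A reader might infer that any missed procedure removes the endpoint; the documents do not support that. Nor can an early stopper both lack an endpoint and have an early one-month visit: those outcomes belong to different readings of the same word.
2. **The 20% is loss to follow-up.** People who cannot be reached are not recovered by rescheduling a visit. Randomization also precedes the stabilization phase, and a 3-day average VAS below 50 then ends participation. Such subjects are untreated and outside the primary set, yet may be part of the 20%. This stands, and makes the 20% row an upper bound. Subjects who stop for lack of relief may also be true failures, so measuring them need not restore 30 points.
3. **Missing data are already addressed.** Tipping-point analysis probes informative missingness directly. True, but neither it nor multiple imputation replaces a value that a willing subject could have given.
4. **Safety is still captured.** A reader might infer that early stoppers escape safety follow-up. The Adverse Events section allows recording at any time during the trial, and the safety analysis covers all randomized subjects. Only the scheduled evaluation may be missed.

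**Conclusion.** The point holds for subjects who stop early. The plan puts them in the primary analysis but gives them either no endpoint and no one-month visit, or both at the wrong time, depending on which section a site follows. For a subject who misses one session but attends the last, it is a conflict of wording and not a certain loss.

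The size cannot be fixed from the documents, because the share who stop treatment but remain reachable is not given (anywhere from 0 to 100% of the 20%). At most, with equal loss in both arms and every such subject scored as a failure, the expected difference falls from 30 to 24 points. This rests on LOCF falling back to baseline. It is not an estimate of what the fix would recover. Nor do the documents support the stronger inference that early stopping will decide the 30-point criterion, since they say nothing about how stopping would divide between arms.

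The change is worth making because the present triggers work against the plan's own intent-to-treat principle and the correction is small.

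**What to change.** Reconcile the Table of Subject Events, Procedure Administration Phase Measures, the one-month visit text and Evaluation Time Points, so that all four use the same rule:

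- **Subjects who complete six procedures:** keep the endpoint within 24 hours after the sixth, including when the sixth is delayed. A single date fixed in advance for everyone would measure a completer whose sessions slipped before the sixth procedure.
- **Subjects who stop early or miss the last procedure:** hold the endpoint visit at the planned date of the sixth procedure (end of week 3, with a stated window), and the one-month visit 30 days after that date.
- **Everyone who received at least one procedure:** is assessed at both visits, with all listed measures and the adverse event evaluation, whatever the number of procedures received, unless consent is withdrawn.

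This concerns measurement only and leaves treatment unchanged. It adds no new type of visit. The cost is protocol wording and the effort of recalling a few subjects who stopped. Their values will reflect incomplete treatment, as an intent-to-treat analysis intends. The documents contain no budget, so no money figure can be given.
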